7.2 PARTICIPANT DISCONTINUATION/WITHDRAWAL FROM THE STUDY

Participants are free to withdraw from participation in the study at any time upon request. Participants will be withdrawn from the study should they experience greater than minimal risk as described in section 2.3.

In addition, an investigator may discontinue a participant from the study for the following reasons:

- Significant study intervention non-compliance, unless varying compliance is an aspect of the study objectives
- Lost-to-follow up; unable to contact subject (see **Section 7.3, Lost to Follow-Up**)
- Participants who become pregnant during the study, as weight loss is contraindicated.
- Any event or medical condition or situation occurs such that continued collection of follow-up study data would not be in the best interest of the participant or might require an additional treatment that would confound the interpretation of the study
- The participant meets an exclusion criterion (either newly developed or not previously recognized) that precludes further study participation

The reason for participant discontinuation or withdrawal from the study will be recorded on the Case Report Form (CRF). Subjects who sign the informed consent form and are randomized but do not receive the study intervention may be replaced. Subjects who sign the informed consent form, and are randomized and receive the study intervention, and subsequently withdraw, or are discontinued from the study, will not be replaced.

The research team will provide continuous monitoring of participant safety and periodic reporting to the UNC IRB as required, including any Unanticipated Problems/Severe Adverse Events that may have occurred during the study. Data safety and monitoring activities continue until all participants have completed trials and until all participants have been followed to the point at which study-related adverse events would likely no longer be encountered.

7.3 LOST TO FOLLOW-UP

A participant will be considered lost to follow-up if they fail to return for the 12-week follow up assessment visit and study staff are unable to contact the participant after at least 3 attempts.

The following actions must be taken if a participant fails to return to the clinic for a required study visit:

- The site will attempt to contact the participant, reschedule the missed visit within 4 weeks of the scheduled time frame, counsel the participant on the importance of maintaining the assigned visit schedule, and ascertain if the participant wishes to and/or should continue in the study.
- Before a participant is deemed lost to follow-up, the investigator or designee will make every effort to regain contact with the participant (where possible, 3 telephone calls and, if necessary, a certified letter to the participant's last known mailing address or local equivalent methods). These contact attempts will be documented in the participant's study file.
- Should the participant continue to be unreachable, he or she will be considered to have withdrawn from the study with a primary reason of lost to follow-up

8 STUDY ASSESSMENTS AND PROCEDURES

8.1 EFFICACY ASSESSMENTS

Note: Refer to the Schedule of Activities 1.3 for the timing and frequency of assessments.

Screening and Orientation

Screening, orientation, and enrollment procedures are described in section 5.5. At each point, study staff will confirm eligibility, as described. The participant has the choice to discontinue participation at any point. If participation is discontinued by staff or the participant, screening information will be held for the duration of the study and identifiers will be destroyed after the study is complete. Reasons for ineligibility will be retained for descriptive purposes.

Physical Measurements

Weight (kg) (primary outcome): Participants will be weighed wearing shorts and without shoes using a calibrated digital Tanita scale. Trained study staff will conduct these measurements following a standardized protocol. Two measures will be completed and the average of the two will be used. If the difference between the two measures exceeds 0.2 kg, a third measure will be taken.

Height (cm): Height will be measured at baseline using a wall-mounted stadiometer (Country Technology Inc, WI). Two measures of height will be taken and the average of the two will be used. If the two measures are not within 0.5 cm, a third measurement will be taken

BMI: Height and weight will be used to calculate BMI.

HbA1c will be measured with a fingerstick and analyzed on a point of care unit (Afinion Alere).

REDCap questionnaires:

Demographics. Participants will provide demographic information at baseline. They will provide age, gender, race/ethnicity, weight, and smoking history. (Baseline only)

Diabetes Specific Locus of Control.

We will administer an 18-item questionnaire consisting of three domains measuring diabetes-specific internal locus of control, powerful other locus of control, and chance locus of control (39).

Diabetes Obstacles Questionnaire. This is a diabetes-related quality of life questionnaire consisting of 30 items using a 5-point Likert-scale addressing social, psychological, cognitive, and behavioral obstacles (40).

Glucose Monitoring System Satisfaction Survey. This is a 15-item survey consisting of four scales including Emotional Burden, Behavioral Burden, Openness, and Trust. The survey is validated in Type 1 and Type 2 diabetes patient populations and assesses satisfaction with the device and its impact on quality of life. We have slightly modified four items to replace "diabetes" with "blood sugar" to better align with our population and research aims (41).

Personal Diabetes Questionnaire. This questionnaire will be used both as a secondary outcome to test the effect of the intervention as well as an assessment tool to inform the counselor at baseline in order to personalize the intervention. The following scales will be used: Weight Change Readiness Dietary Knowledge and Skills, Diet Decision Making, Eating Problems, Diet Barriers, Physical Activity, and Exercise Barriers. This is a validated measure of diabetes self-care behaviors, perceptions and barriers (42).

Technology Acceptance Model-Continuous Glucose Monitoring. This survey assesses usability and predictors of adherence to using the CGM device. Subscales include perceived reliability, information overload, technology-related self-efficacy, usefulness, ease of use, attitude, visibility of body change, and intention. We have added an item to assess helpfulness with weight management (in addition to blood sugar control) (43).

Program Satisfaction. Participants will be asked to complete a post-treatment program evaluation. Questions will ask about participants' perceptions and experiences with the intervention and may provide valuable information about how to modify the programs for future use in this population. Participants will be asked to report their overall satisfaction with the intervention they received. Additional satisfaction questions will assess specific treatment components including the topics of the weekly lessons and use of the app and activity tracker for self-monitoring. Post-intervention only.

Feasibility Measures. Adherence to digital scale use; activity tracking and physical activity patterns captured by the Fitbit; Blood Glucose monitoring and outcomes; Red food monitoring; and attendance at individual counseling sessions will be tracked.

Medical Events. Adverse medical events and changes to medications will be assessed at 12 weeks (staff administered).

8.2 SAFETY AND OTHER ASSESSMENTS

Safety management in this study is intended to achieve 4 objectives: 1) to minimize the occurrence of adverse effects; 2) to effectively manage adverse events as they relate to the study; 3) to identify when the intervention should be suspended because of concerns for participant safety; and 4) to determine when the intervention may be resumed after having been suspended.

Should any concerns arise during data collection, they will be addressed immediately by study personnel and the PI will be notified as soon as possible. Though unlikely, should any concerns arise after data

collection, subjects will be given the study coordinator's contact information to share their concerns and the PI will address concerns directly or through appropriate referrals. Any concerns that arise over the course of the study will be recorded and aggregated as part of the feasibility data and shared with the research team and the IRB as necessary.

We do not anticipate that any questions, anthropometric measurements, observations will cause discomfort or embarrassment, but participants may stop or refuse collection of data at any time. Participants will be informed of potential safety risks in the informed consent.

The research team will provide continuous monitoring of participant safety and periodic reporting to the UNC IRB as required, including any Unanticipated Problems/Severe Adverse Events that may have occurred during the study. Data safety and monitoring activities continue until all participants have completed trials and until all participants have been followed to the point at which study-related adverse events would likely no longer be encountered.

8.3 ADVERSE EVENTS AND SERIOUS ADVERSE EVENTS

8.3.1 DEFINITION OF ADVERSE EVENTS (AE)

This protocol uses the definition of adverse event from 21 CFR 312.32 (a): any untoward medical occurrence associated with the use of an intervention in humans, ***whether or not considered intervention-related.***

8.3.2 DEFINITION OF SERIOUS ADVERSE EVENTS (SAE)

A possible SAE is any event that may meet the following criteria (complete one SAE form for each event):

- a. An event that was life threatening, or placed the participant at immediate risk of death
- b. An event that caused persistent or significant disability or incapacity (lasted at least one month and changed the participant's life)
- c. An event that required or prolonged a hospitalization
- d. A pregnancy that resulted in a congenital anomaly or birth defect
- e. Death
- f. An event that caused other significant hazards or potentially serious harm to research subjects or others

8.3.3 CLASSIFICATION OF AN ADVERSE EVENT

8.3.3.1 SEVERITY OF EVENT

For adverse events (AEs) not included in the protocol defined grading system, the following guidelines will be used to describe severity.

- **Mild** – Events require minimal or no treatment and do not interfere with the participant's daily activities.
- **Moderate** – Events result in a low level of inconvenience or concern with the therapeutic measures. Moderate events may cause some interference with functioning.
- **Severe** – Events interrupt a participant's usual daily activity and may require systemic drug therapy or other treatment. Severe events are usually potentially life-threatening or incapacitating. Of note, the term "severe" does not necessarily equate to "serious".

8.3.3.2 RELATIONSHIP TO STUDY INTERVENTION

All adverse events (AEs) will have their relationship to study procedures, including the intervention, assessed by an appropriately-trained clinician based on temporal relationship and his/her clinical judgment. The degree of certainty about causality will be graded using the categories below.

- **Related** – The AE is known to occur with the study procedures, there is a reasonable possibility that the study procedures caused the AE, or there is a temporal relationship between the study procedures and the event. Reasonable possibility means that there is evidence to suggest a causal relationship between the study procedures and the AE.
- **Not Related** – There is not a reasonable possibility that the study procedures caused the event, there is no temporal relationship between the study procedures and event onset, or an alternate etiology has been established.

8.3.3.3 EXPECTEDNESS

A clinician with appropriate expertise in behavior and physiological adaptation will be responsible for determining whether an adverse event (AE) is expected or unexpected. An AE will be considered unexpected if the nature, severity, or frequency of the event is not consistent with the risk information previously described for the study procedures.

8.3.4 TIME PERIOD AND FREQUENCY FOR EVENT ASSESSMENT AND FOLLOW-UP

The occurrence of an adverse event (AE) or serious adverse event (SAE) may come to the attention of study personnel during study assessment visits and individual coaching sessions.

All AEs, not otherwise precluded per the protocol, will be captured on the appropriate adverse events form. Information to be collected includes event description, time of onset, clinician's assessment of severity, relationship to study procedures (assessed only by those with the training and authority to make a diagnosis), and time of resolution/stabilization of the event. All AEs occurring while on study will be documented appropriately regardless of relationship. All AEs will be followed to adequate resolution.

Any medical or psychiatric condition that is present at the time that the participant is screened will be considered as baseline and not reported as an AE. However, if the study participant's condition deteriorates at any time during the study, it will be recorded as an AE.

Changes in the severity of an AE will be documented to allow an assessment of the duration of the event at each level of severity to be performed. Documentation of onset and duration of each episode will be maintained for AEs characterized as intermittent.

[name] will record events with start dates occurring any time after informed consent is obtained until 7 (for non-serious AEs) or 30 days (for SAEs) after the last day of study participation. At each study visit, the study team will inquire about the occurrence of AE/SAEs since the last visit. Events will be followed for outcome information until resolution or stabilization.

8.3.5 ADVERSE EVENT REPORTING

The research team will report to the UNC IRB as required, including any Unanticipated Problems/Severe Adverse Events that may have occurred during the study. Data safety and monitoring activities continue until all participants have completed the trial and until all participants have been followed to the point at which study-related adverse events would likely no longer be encountered.

8.3.6 SERIOUS ADVERSE EVENT REPORTING

In consultation with the PI, a trained member of the study team will be responsible for conducting an evaluation of a serious adverse event and shall report the results of such evaluation to the reviewing Institutional Review Board (IRB) as soon as possible, but in no event later than 10 working days after the investigator first learns of the event.

8.3.7 REPORTING EVENTS TO PARTICIPANTS

NA

8.3.8 EVENTS OF SPECIAL INTEREST

NA

8.3.9 REPORTING OF PREGNANCY

Participants who become pregnant during the study will be withdrawn and the intervention will be withdrawn as weight loss is contraindicated. Pregnancies will be reported on the Medical Events form, should they occur.

8.4 UNANTICIPATED PROBLEMS

8.4.1 DEFINITION OF UNANTICIPATED PROBLEMS (UP)

This protocol uses the definition of Unanticipated Problems as defined by the Office for Human Research Protections (OHRP). OHRP considers unanticipated problems involving risks to participants or others to include, in general, any incident, experience, or outcome that meets **all** of the following criteria:

- Unexpected in terms of nature, severity, or frequency given (a) the research procedures that are described in the protocol-related documents, such as the Institutional Review Board (IRB)-approved research protocol and informed consent document; and (b) the characteristics of the participant population being studied;
- Related or possibly related to participation in the research (“possibly related” means there is a reasonable possibility that the incident, experience, or outcome may have been caused by the procedures involved in the research); and
- Suggests that the research places participants or others at a greater risk of harm (including physical, psychological, economic, or social harm) than was previously known or recognized.

8.4.2 UNANTICIPATED PROBLEM REPORTING

The investigator will report unanticipated problems (UPs) to the reviewing Institutional Review Board (IRB) and to the lead principal investigator (PI). The UP report will include the following information:

- Protocol identifying information: protocol title and number, PI's name, and the IRB project number
- A detailed description of the event, incident, experience, or outcome
- An explanation of the basis for determining that the event, incident, experience, or outcome represents an UP
- A description of any changes to the protocol or other corrective actions that have been taken or are proposed in response to the UP

To satisfy the requirement for prompt reporting, UPs will be reported using the following timeline:

- UPs that are serious adverse events (SAEs) will be reported to the IRB and to the DCC/study sponsor/funding agency within <insert timeline in accordance with policy> of the investigator becoming aware of the event
- Any other UP will be reported to the IRB and to the DCC/study sponsor/funding agency within <insert timeline in accordance with policy> of the investigator becoming aware of the problem

- All UPs should be reported to appropriate institutional officials (as required by an institution's written reporting procedures), the supporting agency head (or designee), and the Office for Human Research Protections (OHRP) within <insert timeline in accordance with policy> of the IRB's receipt of the report of the problem from the investigator

8.4.3 REPORTING UNANTICIPATED PROBLEMS TO PARTICIPANTS

NA

9 STATISTICAL CONSIDERATIONS

9.1 STATISTICAL HYPOTHESES

- Primary Efficacy Endpoint(s): n/a
- Secondary Efficacy Endpoint(s): n/a

9.2 SAMPLE SIZE DETERMINATION

Sample size was not determined using statistical methods. This was a pilot and feasibility study and the sample size was determined based on funding and logistics.

9.3 POPULATIONS FOR ANALYSES

The analysis population will be Intention-to-Treat (ITT) (i.e. all randomized participants)

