6.3 MEASURES TO MINIMIZE BIAS: RANDOMIZATION AND BLINDING

This is a single arm study. Therefore, randomization is not applicable.

Due to the size of this pilot study and staffing limitations during the COVID-19 pandemic, study staff will not be blinded for the assessments. Assessment staff will be trained and strictly adhere to assessment protocol.

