9.4 STATISTICAL ANALYSES

9.4.1 GENERAL APPROACH

App utilization will be explored using descriptive statistics examining sums of weighing days, tracker wear, days of BG monitoring, and days tracking Red foods. Preliminary analysis of change over time in weight and A1c will be conducted using paired t-tests. Estimates of change on physiologic and psychologic variables, along with others in the literature, will be used to estimate effect sizes for the R01.

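### The analysis population is defined by randomization in a single-arm trial, and a paired t-test with no missing-weight rule yields an observed-pairs result, not the intention-to-treat result named

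*Combined protocol and SAP*

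**What the plan says.** Section 9.3 gives a single analysis population: "The analysis population will be Intention-to-Treat (ITT) (i.e. all randomized participants". Section 6.3 says: "This is a single arm study. Therefore, randomization is not applicable". Section 4.1 also describes a single-arm pilot.

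Section 7.2 makes both of its replacement rules depend on randomization. The first reads: "Subjects who sign the informed consent form and are randomized but do not receive the study intervention may be replaced". The second covers those who sign consent "and are randomized and receive the study intervention, and subsequently withdraw, or are discontinued from the study, will not be replaced".

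The primary endpoint is change in body weight from baseline to 12 weeks (Sections 1.1 and 3). Section 9.4.2 only refers back to 9.4.1, which says: "Preliminary analysis of change over time in weight and A1c will be conducted using paired t-tests". The resulting estimates, "along with others in the literature, will be used to estimate effect sizes for the R01". Section 9 contains no imputation rule, no longitudinal model, no sensitivity analysis and no named completer set.

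Missing 12-week weights are foreseen. Section 7.2 allows withdrawal, and Section 7.3 defines loss to follow-up by the missed 12-week visit. Section 7.1 keeps the final assessment for participants who stop the intervention but stay in the study.

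**The concern.** Two problems are linked. The population is defined by an event that does not occur in this trial, so the reader must supply the definition. And under the sensible definition, all enrolled participants, the named test does not analyse that population unless every 12-week weight is present. A paired t-test needs both weights, so anyone without the second drops out unannounced.

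A result described as intention-to-treat could therefore be a completers result. If people who do not return have done less well, the mean loss is too favourable, and its confidence interval does not show it, because the interval reflects sampling error only. Since the estimate has a stated use in planning a larger trial, the optimism could be carried forward.

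**Working it through.** The plan has no figure to reproduce: Section 9.2 says the sample size was not set statistically, and no mean, SD or dropout rate is given for this trial. N = 20 is from Section 1.1. Values marked as assumed are illustrations.

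**Step 1: who is in the set.** Section 9.3 requires randomization and Section 6.3 rules it out. Section 5.4 places screen failures outside the study. Section 5.5 starts the sessions after the baseline assessments. That leaves one boundary open: whether a participant who was weighed at baseline, never started, and was replaced under Section 7.2 still counts.

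**Step 2: who the test uses.** With m weights missing, the test uses 20 − m pairs and covers everyone enrolled only if m = 0. With an assumed independent chance of a missing weight of 5%, 10% or 20%, the probability that all 20 are present is 0.95^20 = 36%, 0.90^20 = 12% or 0.80^20 = 1.2%.

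**Step 3: size of the error.** Let o be the mean loss in those observed, d the mean loss in those missing, and p = m/20.

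- All-enrolled mean = (1 − p)o + pd
- Error of the observed-pairs mean = p(o − d)
- If d = 0, relative overstatement = p/(1 − p), whatever o is

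With d = 0 (assumed):

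| Missing of 20 | p/(1 − p) | Error at o = 2.4 kg | Error at o = 5 kg |
|---|---|---|---|
| 2 | 0.1/0.9 = 11% | 0.24 kg | 0.50 kg |
| 4 | 0.2/0.8 = 25% | 0.48 kg | 1.00 kg |
| 6 | 0.3/0.7 = 43% | 0.72 kg | 1.50 kg |

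The 2.4 kg is the loss that Section 2.2 reports for the team's 6-month trial in mothers of preschool children. The 5 kg is assumed.

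The direction depends on d. With 4 missing and o = 2.4 kg, the error is 0.2 × (2.4 − d): +0.28 kg for d = 1, +0.08 kg for d = 2, 0 for d = 2.4, and −0.20 kg for d = 3.4.

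**Step 4: scale against sampling error.** With 16 pairs and an assumed SD of 4 kg, the 95% half-width is 2.131 × 4/√16 = 2.13 kg (1.6 to 2.7 kg for SD 3 to 5). The shifts above are smaller than this.

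**Step 5: baseline carried forward as a check.** Setting missing changes to zero gives (1 − p)o, with error −pd. With 4 missing and o = 2.4 kg the estimate is 1.92 kg.

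- If the missing lost 2.4 kg as well, it understates the loss by 0.48 kg.
- If they gained 0.9 kg (the control-group gain in the same Section 2.2 trial), the all-enrolled mean is 0.8 × 2.4 − 0.2 × 0.9 = 1.74 kg, and the check still overstates by 0.18 kg.
- Its interval is too narrow. The zero-filled SD is √[(15 × 16 + 16 × 0.48² + 4 × 1.92²)/19] = 3.69 kg, so the half-width is 2.093 × 3.69/√20 = 1.73 kg against 2.13 kg for observed pairs. The difference arises from treating zeros as measurements.

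**Step 6: effect of the open boundary.** Suppose 20 participants start, 16 have a 12-week weight, and 2 further non-starters were replaced. The zero-change mean is 16 × 2.4/22 = 1.75 kg if the non-starters count and 16 × 2.4/20 = 1.92 kg if they do not.

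**The case against.** The strongest reply is that this is template text in a small pilot. The design is plainly single arm, and anyone would read enrolled for randomized. A reader might infer that the analysis set is empty and the analysis cannot be done. The documents do not support that: the intent is evident, and the correction to that wording is editorial.

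The protocol also works to keep weights from going missing. Section 7.3 provides for rescheduling within 4 weeks, telephone calls and a certified letter. Section 5.5 pays for the 12-week assessment and lets those who complete it keep the devices. Section 10.4 records remote weighing when clinic visits were suspended. These bear on how likely 4 or 6 missing weights would be.

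A reader might also infer that poor adherers will be removed, which would bias the completers. Section 7.2 does list "Significant study intervention non-compliance, unless varying compliance is an aspect of the study objectives", but adherence is an exploratory endpoint in Section 3 and a feasibility measure in Section 8.1, so the exception arguably switches that rule off here.

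Nor do Sections 7.1 and 7.2 contradict each other. The first covers stopping the intervention while staying in the study, and the second covers leaving the study. Some missing weights follow from the plan itself, as where "continued collection of follow-up study data would not be in the best interest of the participant".

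Finally, Section 2.2 describes a pilot in which less frequent weighers lost 0.3% against 4.9% in frequent weighers. It is tempting to read this as showing that dropouts lose less. But it compares participants whose weight change was known, in a weight-gain-prevention study, and says nothing about people with no final weight.

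All this limits the likelihood and size of the problem. None of it says how to analyse a weight that is still missing. The t-test's degrees of freedom would reveal the number of pairs, but not the number enrolled.

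**Conclusion.** The point holds and should be fixed. The stated population is wrong for the design, and the stated test does not deliver the intended one once a 12-week weight is missing.

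Under the assumption that those missing lost nothing, the mean loss is overstated by 11% with 2 of 20 missing and 25% with 4 of 20. It is unbiased if they lost as much as the others and understated if they lost more. The documents establish neither the number missing nor the direction, so this is a conditional risk and not a demonstrated bias.

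The consequence is limited. Section 9.1 states no hypotheses, Section 9.2 makes no power claim, Section 9.4.1 calls the analysis preliminary, and the estimate enters R01 planning together with literature values. No error rate is affected. What is affected is whether a reader can tell whom the estimate describes.

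**What to change.** 1. In Section 9.3, define the set as all eligible, consented participants entered in the study with a baseline weight, regardless of adherence or later discontinuation, with screen failures under Section 5.4 excluded. In Section 7.2, replace *randomized* with *enrolled*, and state whether a non-starter who is replaced still counts.
2. In Section 9.4.2, keep the paired t-test and label it an observed-pairs analysis. Add an all-enrolled sensitivity analysis of the 12-week change with a 95% confidence interval. A likelihood-based repeated-measures model is preferable, using the clinic-session weights (Section 4.1) and home-scale weights (Section 6.1.1) already collected. It assumes that weights are missing at random given those observed, and should acknowledge the two types of scale. Add baseline carried forward as a simple check. It is conservative if those missing lost weight on average, but it is not a worst case, and its interval should not be read as more precise.
3. Report the number enrolled and the number with a 12-week weight, split by clinic or remote scale, and carry both estimates into R01 planning.

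The cost is a few sentences and one or two extra analyses, with no new data collection. The headline loss may turn out less favourable.
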